4.2 Secondary Endpoints

- The daily number of PACs
- The daily number of PVCs
- The daily presence of AF

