	7.1 7.2 7.3 7.4 7.5 7.6 7.7 7.8 7.9 7.10	PARTICIPANT RECRUITMENT MOBILE STUDY ACTIVITIES: MOSIO FOR RESEARCH ECG MONITOR: ZIO® XT PATCH EVENT MONITOR HOME SLEEP APNEA TEST TEXT MESSAGING SERVICE ENROLLMENT VISIT (PRE-SCREENING/PRE-CONSENT) BASELINE VISIT (BEFORE DAY 1) RANDOMIZATION AND MONITORING (DAY 1-14) ASSESSMENT OF SLEEP QUALITY MONITORING CLOSE-OUT VISIT (DAY 15+)	11 12 12 12 13
8	RIS	K AND BENEFIT ASSESSMENT	. 14
	8.1 8.2 8.3	RISKS BENEFITS ASSESSMENT OF POTENTIAL RISKS AND BENEFITS	14
9	DIS	CONTINUATION AND REPLACEMENT OF PARTICIPANTS	. 15
	9.1 9.2 9.3	EARLY DISCONTINUATION FROM RANDOMIZATION. WITHDRAWAL OF PARTICIPANTS FROM THE STUDY. REPLACEMENT OF PARTICIPANTS	16
10	STA	ATISTICAL METHODS AND CONSIDERATIONS	. 16
	10.1 10.2	SAMPLE SIZE AND RANDOMIZATION	

Disrui	oted	Sleep	and	Concurrent	Ectopy or	Atrial	Fibrillation

10.3	Intention-to-Treat (ITT)	16
11 AD	MINISTRATIVE, ETHICAL, REGULATORY CONSIDERATIONS	17
11.1	PROTOCOL AMENDMENTS	17
11.2	Informed Consent Form	17
12 DE	EEDENCES	47

Version Date: 03 June 2025

LIST OF ABBREVIATIONS

AF atrial fibrillation

CFR Code of Federal Regulations

ECG electrocardiogram

HGNS Hypoglossal nerve stimulation
 IEC Independent Ethics Committee
 IRB Institutional Review Board
 PACs Premature atrial contractions

PVCs Premature ventricular contractions

PROTOCOL SYNOPSIS

TITLE	Disrupted Sleep and Concurrent Ectopy or Atrial Fibrillation (DISCRETE AF)				
SPONSOR	Investigator-initiated				
FUNDING ORGANIZATION	UCSF Cardiology and the Heart Rhythm Society				
NUMBER OF SITES	1				
RATIONALE	To examine, in a randomized fashion to allow inference of causal effects, the acute relationship between sleep disruption and atrial and ventricular ectopy.				
STUDY DESIGN	This is a prospective, randomized, case-crossover study.				
GENERAL OBJECTIVE	To assess the acute effects of sleep disruption on clinically relevant cardiac ectopy pertinent to atrial fibrillation (AF).				
SPECIFIC OBJECTIVES	 Primary: To assess the effect of sleep disruption on daily number of cardiac ectopic beats. Secondary: To assess the effect of sleep disruption on daily number of premature atrial contractions (PACs). To assess the effect of sleep disruption on daily number of premature ventricular contractions (PVCs). To assess the effect of sleep disruption on daily number of AF episodes. 				
NUMBER OF PARTICIPANTS	100				

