PARTICIPANT SELECTION CRITERIA	 Inclusion Criteria: Age 21 years or older Have a hypoglossal nerve stimulation (HGNS) device implanted for obstructive sleep apnea and followed up at UCSF Are willing to abstain from using the HGNS device for no more than two consecutive days as instructed over the 14-day trial period Able and willing to provide written informed consent Exclusion Criteria: Currently pregnant or trying to get pregnant Are currently taking Class 1 or 3 anti-arrhythmic medications Have a history of permanent AF or expected to have AF throughout the study period 				

Version #: 1.1 Version Date: 03 June 2025 Page 6 of 21

	 Have congenital heart disease Are >40% ventricular paced Are unable to read or sign to provide informed consent 				
STUDY DURATION	Participants will participate for approximately 2 weeks. • Randomization and monitoring: up to 2 weeks.				
PROCEDURE	After being fitted with an automatically recording electrocardiographic monitor, the HGNS device will then be "on" versus "off" (where "off" is turning off the HGNS device for one night and "on" is turning on the HGNS device) over the ensuing 14 days. Participants will be randomized to "off-on" versus "on-off" periods, assuring no more than two consecutive days of either device use or not. Electrocardiographic monitoring data will be used to assess for endpoints.				
PRIMARY ENDPOINT	The daily number of cardiac ectopic beats				
SECONDARY ENDPOINTS	 The daily number of PACs The daily number of PVCs The daily presence versus absence of AF episodes ≥ 30 seconds 				
STATISTICS Primary Analysis Plan	Our primary analyses will employ intention-to-treat principles, examining randomization assignment as the primary predictor.				
Rationale for Number of Participants	Using a two-tailed alpha of 0.05, we estimate we will need 100 participants to have 80% power in intention-to-treat analyses comparing nights on and off HGNS to detect a 2% increase in cardiac ectopy.				

Version #: 1.1 Version Date: 03 June 2025 Page 7 of 21

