1 INTRODUCTION

1.1 BACKGROUND

Sleep disorders and poor sleep are a major public health problem owing to their prevalence and adverse effects. One health condition that sleep disorders have long been implicated in is the development of AF. AF is the most common sustained cardiac arrhythmia. In a recent study, we estimated that the current US national prevalence of diagnosed AF is at least 10.55 million, comprising 4.48% of the adult population, substantially exceeding prior projections. AF is a leading cause of stroke, reduces quality of life, increases risks of myocardial infarction and dementia, and results in > \$28 billion in US healthcare expenditures annually.

The relationship between poor sleep and incident AF was initially attributed to a common association with obstructive sleep apnea (OSA). However, emerging evidence suggests that chronic sleep disruption independent of OSA may play a role in the development of AF. Indeed, work largely from our group has revealed that abnormal sleep characteristics including frequent nighttime awakening, less rapid eye movement (REM) sleep, and a diagnosis of insomnia may predict incident AF, even after adjustment for OSA.^{4,5} Furthermore, studies of the circadian variation of arrhythmia onset patterns in patients with AF have shown a nocturnal predominance, suggesting that nocturnal events such a disrupted sleep may be arrhythmogenic.^{6,7} Whereas the available evidence mostly support chronic sleep disruption as a risk factor for incident AF, less is known about the near-term risk of a discrete AF episode following a night of disrupted or poor-quality sleep.

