2.2 Specific Objectives

- Primary:
 - To assess the effect of sleep disruption on daily number of cardiac ectopic beats.
- Secondary:
 - o To assess the effect of sleep disruption on daily number of PACs.
 - o To assess the effect of sleep disruption on daily number of PVCs.
 - To assess the effect of sleep disruption on the daily presence versus absence of AF.

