10.2 Statistical Analysis Plan (SAP) and Outcome Assessment

Our primary analyses will employ intention-to-treat principles, examining randomization assignment as the primary predictor. Secondary analyses will examine "per-protocol" compliance, which will also allow for quantitative assessments of outcomes per the number of hours off hypoglossal stimulation as the predictor. We will employ logistic regression with robust standard errors (to take clustering within individuals into account) for the dichotomous presence or absence of outcomes (such as at least one daily PAC, PVC, or episode of AF), and a negative binomial model to assess number of daily events.

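### The AF secondary endpoint is stated in incompatible forms, and daily presence, read literally, can score one episode on two days that usually carry opposite assignments

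*Protocol*

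**What the plan says.** Four places in the protocol state the AF objective or endpoint:

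- Synopsis, Specific Objectives: "To assess the effect of sleep disruption on daily number of AF episodes".
- Synopsis, Secondary Endpoints: "The daily presence versus absence of AF episodes ≥ 30 seconds".
- Section 2.2: "To assess the effect of sleep disruption on the daily presence versus absence of AF".
- Section 4.2: "The daily presence of AF".

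Section 10.2 plans two kinds of model. For counts it names "a negative binomial model to assess number of daily events", without saying whether AF episodes are among those events. For yes/no outcomes it plans logistic regression with robust standard errors, and here AF is given as an example: "for the dichotomous presence or absence of outcomes (such as at least one daily PAC, PVC, or episode of AF".

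The question behind the endpoint is put in Section 1.1: "less is known about the near-term risk of a discrete AF episode following a night of disrupted or poor-quality sleep". Section 8.3 likewise speaks of how AF episodes start. Sections 6.2 and 7.8 assign the device in randomised off-on or on-off pairs over 14 days, a scheme chosen to make switches frequent.

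**The concern.** A count, a presence with a duration threshold and a presence without one are three different variables. The first would go to a different model from the other two. The trial is not blinded (Section 3.1), so leaving this open allows the AF result to be chosen after the data are seen.

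The second issue is the match between endpoint and question. The stated interest is whether a disrupted night sets off a discrete episode. Presence also registers an episode that began earlier and is still running. Because the design switches assignment so often, the day into which an episode runs usually has the opposite assignment, and the event is then credited to the wrong condition.

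**Working it through.** **1. The definitions side by side**

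| Place | Variable | Duration threshold | Model under Section 10.2 |
|---|---|---|---|
| Synopsis objective | count per day | none | negative binomial, if taken literally |
| Synopsis endpoint | yes/no per day | 30 seconds | logistic |
| Section 2.2 | yes/no per day | none | logistic |
| Section 4.2 | yes/no per day | none | logistic |

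Being named as a logistic example does not exclude AF from the count model. PACs and PVCs stand in the same bracket, and both are count endpoints in Section 4.2.

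**2. How often the assignment switches**

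Fourteen days in 7 pairs give 13 day-to-day transitions. The 7 within pairs always switch. The 6 between pairs switch with probability 1/2. The expected number of switches is 7 + 6 × 1/2 = 10 (range 7 to 13), so q = 10/13 = 0.769.

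**3. Effect of carry-over under presence scoring**

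The protocol gives no AF rate, effect size or episode duration, so there is no planned AF figure to reproduce; the power statement in Section 10.1 concerns ectopy. Let RR be the true off/on ratio of onsets. Let p be the fraction of episodes running into the next day, an assumption taken as equal in both conditions. With the on-day onset rate set to 1, and ignoring overlaps and carry-over beyond one day:

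- on-day presence = 1 + p[q·RR + (1 − q)]
- off-day presence = RR + p[q + (1 − q)·RR]

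Direction: off − RR × on = p·q·(1 − RR²). This is negative whenever RR > 1 and p > 0, so the apparent ratio is below RR. If RR < 1 the sign reverses, so the pull is again toward 1. At p = 0 there is no effect.

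Size, worked for RR = 2 and p = 0.10: on = 1 + 0.10 × (1.538 + 0.231) = 1.177; off = 2 + 0.10 × (0.769 + 0.462) = 2.123; ratio = 1.80. The same formulas give:

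| p (assumed) | true 2.0 appears as | true 1.5 appears as |
|---|---|---|
| 0 | 2.00 | 1.50 |
| 0.01 | 1.98 | 1.49 |
| 0.10 | 1.80 | 1.42 |
| 0.25 | 1.60 | 1.32 |
| 0.50 | 1.39 | 1.22 |

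**4. Check by simulation**

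The check used 200,000 participants per scenario under the protocol's pair scheme. Its assumptions were 2% daily onset on on days, a rate ratio of 2, and probability c that AF present on one day continues into the next, so multi-day episodes are possible. Scoring by onset gave odds ratios of 2.02 to 2.05. Scoring by presence gave 2.03 (c = 0), 1.92 (0.05), 1.83 (0.10), 1.61 (0.25), 1.33 (0.50) and 1.15 (0.75). Direction and rough size agree with the formula.

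**The case against.** Three of the four statements agree on a binary daily endpoint, including both sections in the body. The count appears in one synopsis line, and Section 4.2 can be read as shorthand for the synopsis endpoint. Section 10.2 names AF only under the logistic model. This narrows the conflict but does not remove it: the threshold stands in one place only, and nothing bars the count. An analysis plan that is not shown could settle the choice only by departing from one of these lines.

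A reader might infer that the trial will in fact count episodes twice and that its AF effect will be materially diluted. The documents do not support that. No section says how an episode crossing the day boundary is scored. The wording in Section 10.2 is compatible with attributing an episode to the day it starts, and boundary rules may properly sit in the analysis plan. Nor does the protocol give any AF duration, so no value of p has support. AF is not required for entry, and the synopsis excludes permanent AF or AF expected throughout, which would limit long episodes. The exclusion list in Section 5.2 lacks that item, so the two lists need reconciling.

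Presence versus onset is also partly a choice of what to estimate. Section 1.2 cites an association between worse sleep and longer AF episodes the next day, and presence can pick up some of that. This stands, and is the reason to keep presence as a sensitivity analysis.

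**Conclusion.** The inconsistency is established by the text alone: count against presence, and a 30-second threshold given once. It should be corrected before data are seen. It touches a secondary endpoint only; the primary analysis is unaffected.

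The dilution holds in direction and conditionally: if presence is scored literally and some episodes cross the day boundary, the contrast moves toward 1, because 77% of transitions switch assignment on average. Its size is not known. It ranges from nothing, when episodes are short, to 1.80 for a true 2.0 at an assumed 10% carry-over, and further at higher assumed values. It should be reported as a risk of the wording, not as a bias shown to exist in this trial.

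**What to change.** Use one definition in the synopsis objective, the synopsis endpoint, Section 2.2 and Section 4.2: at least one AF episode of 30 seconds or more with onset in the 24-hour period that begins with, and includes, the assigned night. Attribute each episode once, to the period in which it starts, and analyse with the logistic model already planned. State in Section 10.2 that the negative binomial model does not apply to AF.

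Two details matter. The period must include the assigned night: a window opening only afterwards would miss AF that starts during that night and take in the next night, which usually has the opposite assignment. All randomised days should stay in the main analysis, in line with Section 10.3, because dropping periods that begin in AF would select on an outcome arising after randomisation. Report two sensitivity analyses: any-presence scoring, and exclusion of periods that begin in ongoing AF.

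The cost is wording. Onset times come from the continuous ECG recording already planned (Section 7.3). There are two downsides. Onset scoring does not capture prolongation of episodes, which any-presence scoring partly covers. A period spent wholly in ongoing AF counts as having no onset, and the second sensitivity analysis will show how much that matters.

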5 PARTICIPANT SELECTION

5.1 Inclusion Criteria

Participants must meet all the following to be eligible:

- Are age 21 years or older
- Have a HGNS device implanted for OSA and followed up at UCSF
- Are willing to abstain from using the upper airway stimulation device for no more than two consecutive days as instructed over the 14-day trial period
- Able and willing to provide written informed consent

5.2 Exclusion Criteria

- Currently pregnant or trying to get pregnant
- Are currently taking class 1 or 3 anti-arrhythmic medications
- Have congenital heart disease
- Ventricular pacing >40%
- Are unable to read or sign to provide informed consent

6 STUDY INTERVENTIONS

6.1 Hypoglossal Nerve Stimulation Therapy

HGNS is performed by the Inspire Upper Airway Stimulation (Inspire Medical Systems, Inc., Golden Valley, Minnesota, US), a fully implanted system that is placed under the skin of the neck and chest. A remote system can be used to turn the device on or off at nighttime. When sleeping, the device stimulates the tongue, increasing muscle tone and opening the airway in sleep. HGNS has been shown to lead to significant improvements in sleep apnea, sleepiness, and quality of life in patients with OSA.^{23, 24} The use of HGNS by these patients significantly improves their sleep with a reduction in sleep disruption, and those with the implant have met all clinical indications for the device. No participant will have a device placed solely for the purpose of study participation and all will already have

a device implanted per standard clinical indications. A night on HGNS will be considered as reduced sleep disruption, whereas a night off HGNS will be considered one with more sleep disruption.

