7.8 Randomization and Monitoring (Day 1-14)

At 08:00 AM on the first day (Day 1), the participant will receive a text or push notification from a mobile app or text messaging service with instructions for the same day's randomization. Their first reminder regarding their randomization will be at 08:00 PM on Day 1. During the study (Day 1-14), participants will receive two text or push notifications (AM and PM) each day:

- 1. 08:00 AM: Instructions on the present day's randomization, in addition to daily surveys on randomization compliance and sleep quality.
- 2. 08:00 PM: Reminder of instructions on the present day's randomization.

At 08:00 AM on Day 15 participants will complete the final compliance survey and will be reminded to resume their normal HGNS use.

"On" day messages will instruct participants to use their HGNS device and on "off" days, participants will be instructed to not used them. To avoid >2 consecutive days with or without using their device, participants will be randomized in pairs of either "off one day and on the next day" or "on one day and off the next day".

Each participant will also undergo two consecutive days of home sleep apnea recording using the WatchPAT® ONE-M Home Sleep Apnea Test, ideally during the first days of participation.

Throughout the study period (Day 1-14), the participants should continuously wear their ECG monitor.

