8 RISK AND BENEFIT ASSESSMENT

8.1 Risks

Potential risks of the study include the following:

- *Small risk of loss of privacy*: Data that the participant provides to the study may be sensitive and could be embarrassing to participants or lead to insurance coverage problems if it were leaked (e.g., obesity or very high blood pressure).
- *Financial risk*: Participating in the study may make participants want to access the healthcare system more often or purchase health-related devices to link to the study, and that all costs money.
- *Risks of study sensors*: Allergy to the adhesive used for the event monitor electrodes can lead to a rash, pruritus, and/ or painful irritation. Topical steroids will be provided if needed and participants will be provided an option to decline if they are concerned given past experience. As with previous studies, sensors may be moved and/ or not worn if irritation is not tolerable (in which case, late screenfailures and alternative/ additional participants may be used for replacement).
- Risks of HGNS withdrawal: as expected participants may experience an increase in sleep disruption on the days their device is off, potentially leading to a relapse of their OSA symptoms. There should be no long-term effects of therapy withdrawal. Indeed, a previous study showed that 1-week continuous withdrawal of therapeutic HGNS results in acute worsening of both objective and subjective measures of sleep and breathing, but with return of the positive therapeutic effects upon resuming therapy. To limit the acute negative impact of the withdrawal therapy on their well-being, no participant will be instructed to turn off their device more than 7 out of the 14 participation days. It is also part of standard of care

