The Investigators have weighed the adequacy of protection against the importance of knowledge gained and determined the risks to be justified. Whether sleep disruption can truly result in any given AF event remains unknown—in fact whether AF can be triggered by any modifiable exposure has not yet been proven in a randomized trial. The importance of the knowledge to be gained from this study is therefore two-pronged: first, the acute effects of sleep disruptions are relevant to the third of the US population who have insufficient sleep. Second, understanding the mechanism that results in the initiation of AF episodes, or the development of incident AF is relevant to the rapidly growing and large number of AF patients because it will reveal mechanisms germane to AF itself. All taken together, the minimal risks incurred by study participants are reasonable considering the broadly applicable knowledge to be gained.

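### The randomised contrast is a night without HGNS, which worsens breathing as well as sleep, so objectives worded as the causal effect of sleep disruption go beyond what the design supports

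*Protocol*

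**What the plan says.** **What is randomised.** Sections 6.2 and 7.8 randomise the device setting in two-night pairs, off then on or on then off, over 14 days. Eligibility under Section 5.1 requires an implant for OSA ("Have a HGNS device implanted for OSA and followed up at UCSF"). Section 10.2 makes randomised assignment the primary predictor, and its secondary predictor is hours off stimulation.

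**What the contrast is called.** Section 6.1: "a night off HGNS will be considered one with more sleep disruption".

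**What is to be inferred.** The synopsis rationale gives randomisation as the means to causal inference about sleep disruption and ectopy. The Section 2.1 hypothesis, and the primary and all three secondary objectives in Section 2.2, name sleep disruption as the cause under study. None names HGNS withdrawal or the return of OSA. Section 8.3 adds that "the acute effects of sleep disruptions are relevant to the third of the US population who have insufficient sleep".

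**What an off night does.** Section 6.1 says that "the device stimulates the tongue, increasing muscle tone and opening the airway in sleep" and that "HGNS has been shown to lead to significant improvements in sleep apnea, sleepiness, and quality of life in patients with OSA". Section 8.1 says that a week of withdrawal "results in acute worsening of both objective and subjective measures of sleep and breathing", and it warns that OSA symptoms may return on off nights.

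**The concern.** A randomised comparison supports a causal statement about the factor that was randomised. Here that factor is the device setting. Turning the device off removes airway support and, with it, the benefit to sleep. The objectives name only the second of these.

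If ectopy rises on off nights, the report as now framed would present randomised evidence that sleep disruption triggers ectopy. The same rise could come from obstructed breathing, from disturbed sleep, or from both. The difference matters most for Section 8.3. Carrying the result to people who sleep too little but have no OSA requires the effect to run through sleep, and the design cannot show that.

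**Working it through.** The point does not turn on a figure, so the check sets the protocol's statements side by side.

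**Step 1: how many factors are randomised?** One, with two levels (Sections 6.2 and 7.8). No arm or period disturbs sleep while the airway stays treated, and none does the reverse.

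**Step 2: what does that factor change?** By Section 6.1, airway opening, apnea and sleepiness. By Section 8.1, sleep and breathing together. Both components therefore move with assignment.

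**Step 3: does the protocol treat the two as one exposure?** No. Section 1.1 says the link between poor sleep and AF was first put down to OSA, and then that "chronic sleep disruption independent of OSA may play a role in the development of AF". If disruption can act apart from OSA, the two are distinct exposures, and the operational label in Section 6.1 cannot turn a contrast that moves both into a contrast of one.

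**Step 4: does any planned analysis separate them?** No. Assignment and hours off stimulation (Section 10.2) are both measures of device exposure. The planning target in Section 10.1, a 2% increase with 100 participants at 80% power, is stated for nights on versus off HGNS. It describes the total contrast and says nothing about its components.

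**Step 5: could the other data separate them?** Not with the protection of randomisation. Nightly sleep quality is a five-level self-report (Section 7.9) in an unblinded trial (Section 3.1). Apnea is recorded on two consecutive days only (Section 7.4), ideally early in participation (Section 7.8). These data can describe what changed. An analysis that used them to divide the effect would be an exploratory, non-randomised mediation analysis.

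**Step 6: do the two apnea nights give an on/off comparison within each person?** Only if they fall inside one randomised pair. Fourteen nights make 7 pairs and 13 windows of two consecutive nights: 7 within a pair and 6 straddling two pairs. A within-pair window always has one on and one off night. For a straddling window, such as Days 2-3, the possibilities are:

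| Pair 1 | Pair 2 | Night 2 | Night 3 |
|---|---|---|---|
| off-on | off-on | on | off |
| off-on | on-off | on | on |
| on-off | off-on | off | off |
| on-off | on-off | off | on |

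In 2 of the 4 combinations both nights share an assignment. If the two orders are equally likely and independent between pairs (an assumption; the protocol gives no probabilities), half of straddling windows give no within-person comparison. The count follows the pairing rule in Section 7.8; Section 8.3 words the limit on consecutive off nights differently.

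**The case against.** **The contrast is disclosed.** The on/off comparison is stated plainly in the synopsis and in Sections 3.1, 6.2, 7.8 and 10.1, and Section 6.1 says openly that an off night will be considered a more disrupted one. No careful reader would mistake what is randomised. This stands, but it concerns disclosure of the procedure. The objectives still name a different cause, and no section states the limitation.

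**The protocol never claims independence from apnea.** The Section 1.1 sentence concerns chronic disruption and incident AF, and the gap named next is near-term risk after poor sleep, with no independence condition. Section 1.2 also places the study beside earlier randomised trials of sleep apnea treatment. This is right as far as it goes: a reader might infer that the protocol promises an OSA-independent effect, and it does not. The point is narrower. An unqualified effect of sleep disruption is claimed from a contrast that also changes breathing.

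**There is no final conclusion to attack.** The protocol gives a rationale, a hypothesis and objectives, and Section 8.3 is one sentence of relevance in a risk-benefit argument. This is also correct. The fault lies in the stated aim and in that sentence, not in a reported result.

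**Section 7.4 may look like an acknowledgement.** A reader might take the recording of the apnea index and oximetry as a sign that the authors foresaw the problem. Section 7.4 gives no such reason, so nothing is rested on it.

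**Conclusion.** Wrong as written: the protocol claims a causal property that the design does not have. Randomisation validly identifies the total effect of a night without HGNS (under intention to treat, of being assigned one) in HGNS-treated OSA patients. It does not identify the part due to sleep disruption as distinct from recurrent airway obstruction. The objectives, the causal rationale and the Section 8.3 extension therefore go further than the contrast allows.

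Two stronger readings should be resisted. The first is that the trial is confounded or unsound; it is sound for the on/off question, and its randomisation and primary predictor need no change. The second is that the effect can be divided numerically, for instance by assigning a share of the 2% to apnea and the remainder to sleep. The documents do not support such a split. Returning obstruction plausibly causes the off-night sleep disruption, so these are not separate parallel paths whose shares add up, and the 2% is a planned detectable increase, not an estimate. No size is therefore given.

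The conclusion rests on the protocol's own account that withdrawal worsens both sleep and breathing, and on no outside figure.

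**What to change.** 1. Restate the synopsis rationale and objectives, the Section 2.1 hypothesis and the Section 2.2 objectives as the effect of a night without HGNS, meaning the return of OSA with its sleep disruption, in HGNS-treated OSA patients. This matches the wording already used in Section 10.1. Sentences in Sections 1.2 and 8.2 that speak of the direct impact of sleep disruption should follow.
2. Remove the Section 8.3 sentence on people with insufficient sleep, or limit it to a hypothesis for later study.
3. In Sections 7.4 and 7.8, fix the two home sleep apnea recordings within one randomised pair, for example Days 1-2, so that each participant contributes one on and one off night.
4. Report the apnea index, oximetry and sleep-quality rating by assignment beside the primary result, as description only, and state that any mediation analysis is exploratory and non-randomised.

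The cost is protocol wording, a timing rule for a test already planned, and one descriptive table from data already collected. Sample size, endpoints and the primary model are untouched. The real downside is a narrower headline claim.
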